## **Background and Rationale**

Patients undergoing hemodialysis experience multiple physical and psychological challenges, with depression and anxiety being highly prevalent. These psychological burdens negatively affect quality of life, treatment adherence, and long-term outcomes. While pharmacological treatments are commonly used, non-pharmacological interventions such as exercise have shown promising benefits in improving mental health.

However, structured facility-based exercise programs are often inaccessible to many dialysis patients due to physical, logistical, and economic limitations. Home-based exercise programs, which are low-cost and simple to implement, may represent a feasible alternative. This study aims to assess the effect of a home-based walking exercise program on reducing psychological distress among patients undergoing hemodialysis.

## **Study Aim and Objectives**

**Aim:** To investigate the effectiveness of a non-pharmacological, home-based exercise program in reducing psychological distress, depression, and anxiety in patients undergoing hemodialysis.

**Objectives:**

1. To assess the baseline level of psychological distress among patients undergoing hemodialysis.
2. To evaluate the effectiveness of a home-based walking exercise program in reducing depression and anxiety scores compared to a control group receiving standard care.

## **Hypotheses**

**H1:** There is a high level of psychological distress among patients undergoing dialysis treatment.

H2: Home-based exercise intervention significantly reduces psychological distress (depression and anxiety scores) compared to standard care.

## **Study Design**

This research will be conducted in two main phases:

Phase I: Cross-sectional study to assess baseline levels of depression and anxiety using validated tools.

Phase II: Randomized controlled trial (RCT) with two groups:

- Intervention Group: Receives structured, home-based walking exercise program for 6 months.
- Control Group: Receives standard care without exercise intervention.

Post-intervention assessment will be conducted for both groups after 6 months using the same tools.

## **Study Population**

Inclusion Criteria: Adults  $\geq 18$  years old; Diagnosis of ESRD on hemodialysis for  $\geq 3$  years; Stable clinical status; No diabetic foot complications; Able to walk without assistance.

Exclusion Criteria: Any acute or chronic condition limiting participation in exercise; Refusal to give informed consent.

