## **Sample Size and Sampling Technique**

Using Cochran's formula for finite populations, with a total population of 132, a 95% confidence interval, 5% margin of error, and an estimated prevalence of depression of 73%, the calculated sample size is 54 participants.

Sampling Method: Simple random sampling from the list of eligible patients at Al Suwaiq Renal Dialysis Center.

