The Effect of Non-Pharmacological (Home-Based Exercise) Intervention on Psychological Distress of Patients Undergoing Hemodialysis at Al Suwaiq Renal Dialysis Center

NCT07083843

Date:15/08/24

Study Objectives

Primary Objective: To evaluate the effect of home-based exercise on reducing psychological distress (depression and anxiety) in patients undergoing hemodialysis.

Secondary Objective: To describe the baseline prevalence and severity of depression and anxiety among hemodialysis patients.

Study Design

Phase I: Cross-sectional assessment of depression and anxiety levels using the University of Michigan Depression Center's tools.

Phase II: Randomized controlled trial (RCT) with intervention and control groups.

Phase III: Post-intervention reassessment after 6 months.

Study Population

Sample size: Initially 132 screened → 54 enrolled → 26 participants per group in final analysis.

Inclusion/Exclusion Criteria: As defined in the study protocol.

Variables

Primary Outcomes: Depression Score (0-27) using PHQ-9 scoring; Anxiety Score (0-21) using GAD-7 scoring.

Independent Variable: Intervention group assignment (Home-based exercise vs. Control).

Covariates: Age, gender, duration of dialysis, comorbidities.

Data Collection Method

Face-to-face interviews for questionnaire administration. Baseline data from Al Shifa system (demographics, clinical history).

Statistical Analysis

- Data Management: Data entry and cleaning in SPSS v22. Descriptive statistics for demographics and baseline variables: Continuous variables: Mean ± SD (or median and IQR if non-normal). Categorical variables: Frequencies and percentages.
- Baseline Comparisons: Independent t-test, Chi-square, or Fisher's exact test for categorical variables.

Main Analysis: Paired t-test for within-group changes; Independent t-test for between-group differences in change scores.

- Significance Level: p-value < 0.05 considered significant; two-tailed tests.

- Handling Missing Data: Intention-to-treat principle; Last Observation Carried Forward method for missing values.

Presentation of Results

Tables for baseline demographics, pre- and post-intervention scores. Paired t-test results with mean difference, 95% CI, and p-value. Graphical representation of score changes.

Ethical Considerations

Analysis will be performed on anonymized datasets. Results will be reported in aggregate without identifying participants.

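### PHQ-9 and GAD-7 are scored before randomisation, but the scores are used neither to balance the arms nor as covariates in the test of H2

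*Protocol*

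**What the plan says.** - **Question.** Protocol, Hypotheses, H2: "Home-based exercise intervention significantly reduces psychological distress (depression and anxiety scores) compared to standard care". The Protocol's aim and the SAP's primary objective are stated for patients undergoing hemodialysis in general.
- **Entry.** Protocol, Study Population: adults with at least 3 years on hemodialysis, then "Stable clinical status; No diabetic foot complications; Able to walk without assistance". Exclusions are exercise-limiting conditions and refusal of consent. No symptom score is required. Patients are drawn from the eligible list by simple random sampling (Sample Size and Sampling Technique).
- **Timing of the scores.** Protocol, Study Design: "Phase I: Cross-sectional study to assess baseline levels of depression and anxiety using validated tools". The randomised phase follows, so the scores exist before allocation.
- **Outcomes.** SAP, Variables: "Depression Score (0-27) using PHQ-9 scoring; Anxiety Score (0-21) using GAD-7 scoring". Both scales stop at 0.
- **Analysis.** SAP, Main Analysis: paired t-tests within arms and an independent t-test on change scores between arms. The listed covariates are age, gender, duration of dialysis and comorbidities. Baseline PHQ-9 and GAD-7 are not among them, and a t-test would not use covariates in any case.
- **Planning prevalence.** Protocol, Sample Size and Sampling Technique: "an estimated prevalence of depression of 73" per cent. The cut-off that defines depression is not stated, and no prevalence of anxiety is given.

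**The concern.** The baseline score is likely to be an important predictor of how far a patient's score can fall over 6 months. A low scorer is near the floor, and a high scorer has both more room to improve and more regression toward the mean. With about 54 patients and no stratification, chance can give one arm clearly more high scorers than the other. The planned change-score t-test then carries that difference into the estimated effect of exercise. It also leaves in the error term variation that an available measurement could remove.

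A second issue is interpretation. Entry is open at any score, so the between-group difference averages over patients with much and with little room to improve. Without a prespecified estimate by baseline severity, a null result would be hard to read.

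**Working it through.** **Inputs from the documents.** n = 54, N = 132 and prevalence 0.73 (Protocol, Sample Size and Sampling Technique); 26 per group analysed and two-sided alpha of 0.05 (SAP). **Assumptions.** Allocation of 27/27, since no ratio is stated; the effect sizes and SDs in steps 4 and 5, since the documents give none.

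**1. The plan's own figure.** The stated inputs are "with a total population of 132", "a 95% confidence interval, 5% margin of error" and 73%. Cochran: n0 = 1.96² × 0.73 × 0.27 / 0.05² = 302.9. Finite-population correction: 302.9 / (1 + 301.9/132) = 92.1, so 92 or 93 by rounding. The Protocol reports that "the calculated sample size is 54 participants", which does not follow from its inputs. That is a separate matter; 54 is used below only as the planned headcount.

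**2. Patients below the cut-off.** 54 × 0.27 = 14.6, about 15, leaving 54 × 0.73 = 39.4, about 39, at or above it. If 73% is right, the number below would range over about 10 to 20 (hypergeometric, sampling 54 from 132) or 8 to 21 (binomial).

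**3. Chance imbalance.** Let X be the number of the 39 who fall in one arm of 27. X is hypergeometric with population 54, 39 marked and 27 drawn. P(X ≥ 22 or X ≤ 17) = 0.224. In a 22/17 split the shares are 22/27 = 81% and 17/27 = 63%, a gap of 5/27 = 18.5 percentage points.

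**4. What the imbalance does to a change-score comparison.** If patients above the cut-off fall by δ points more than those below, whatever their arm, a 22/17 split shifts the between-arm difference by 0.185 × δ. For assumed δ of 2 to 4 points the shift is 0.37 to 0.74 PHQ-9 points. Subtracting the baseline does not remove it, because δ is a difference in change.

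**5. How far open entry could matter for power.** Assume a true effect of 4 PHQ-9 points and an SD of change of 5 in depressed patients (d = 0.80), 27 per arm, noncentral t.

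| Patients below the cut-off (27%) | Mean effect, points | Power |
|---|---|---|
| None: all are above it | 4.00 | 82% |
| Half the effect | 4 × 0.865 = 3.46 | 70–79% |
| No effect | 4 × 0.73 = 2.92 | 53–62% |

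Each range spans an SD of change of 5 (lower power) to 2.5 (higher power) in the patients below the cut-off. At the SAP's 26 per arm the rows become 81%, 68–77% and 52–60%.

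**6. Testing only the patients above the cut-off.** With 20 versus 19 patients and d = 0.80, power is 68%. That is below the half-effect range for all patients and only modestly above the no-effect range.

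**The case against.** Three stronger readings are tempting, and the documents do not support them.

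*That about 15 patients have no depression to reduce.* The 73% is a planning prevalence at an unstated cut-off, not a Phase I result. A patient below the cut-off can still have several PHQ-9 points to lose. H2 also covers anxiety, for which no prevalence is given, so 15 is not the number without distress.

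*That Phase II ignores the scores.* The SAP's paired tests and change-score comparison both need the baseline score, and the secondary objective reports it. What is missing is its use in allocation or as a covariate.

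*That entry should be restricted, or any claim based on distressed patients alone.* The aim names hemodialysis patients in general, and H1 expects distress to be high. For that population the average over all randomised patients is the quantity of interest and is not an understatement. The subgroup of about 39 is also no cure for low power (step 6).

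It can also be said that a 22/17 split is ordinary chance variation, already covered by the test's error rate. This is true: over repeated randomisations the comparison is unbiased and its type I error is controlled. But this trial will be one randomisation, and the imbalance and the added variance can be avoided with data already in hand.

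**Conclusion.** The concern holds as a matter of efficiency and interpretability, not as a bias in the design. The scores are available before allocation, yet they neither balance the arms nor adjust the comparison. The firm figures, conditional on the 73% and a 27/27 split, are about 15 of 54 patients below the cut-off and a 22% chance of a 22/17 split or worse. The resulting shift in the estimate and the power figures rest on assumed effects and SDs; the power loss from open entry runs from about 3 to 29 percentage points, and the documents cannot narrow it. In a simulation with assumed score distributions, stratifying on Phase I PHQ-9 cut the standard error of the planned change-score comparison by about 9%, and adjusting for the baseline score improved precision further. The 9% is indicative only. The dilution for GAD-7 is unknown.

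**What to change.** 1. **Protocol, Study Design, Phase II:** stratify the randomisation by Phase I PHQ-9, at or above versus below a stated cut-off.
2. **SAP, Main Analysis:** replace the between-group t-test on change scores with an ANCOVA of the 6-month score on arm and the continuous baseline score of the same scale, for PHQ-9 and GAD-7 separately. At the least, include the stratum in the comparison, so that the standard error reflects the stratified allocation. Add the baseline scores to the covariate list.
3. **Population:** state that all randomised patients are the primary population. Between-group differences among patients at or above stated PHQ-9 and GAD-7 cut-offs may be prespecified as secondary, supportive estimates.

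The cost is a two-stratum allocation list, a stated cut-off and slightly more analysis work. If the subgroup estimates are added, they are two comparisons; the PHQ-9 one rests on about 39 patients, and the size of the GAD-7 one is not known in advance.

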## **Sample Size and Sampling Technique**

Using Cochran's formula for finite populations, with a total population of 132, a 95% confidence interval, 5% margin of error, and an estimated prevalence of depression of 73%, the calculated sample size is 54 participants.

Sampling Method: Simple random sampling from the list of eligible patients at Al Suwaiq Renal Dialysis Center.

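### The stated Cochran inputs give about 92 participants, not 54, and no calculation sizes the randomised comparison that the SAP makes primary

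*Protocol*

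**What the plan says.** The Protocol's section on sample size and sampling technique contains the only sample-size calculation in either document. It names the method ("Using Cochran's formula for finite populations"), the population ("with a total population of 132") and a 95% confidence level, and ends with "5% margin of error, and an estimated prevalence of depression of 73%, the calculated sample size is 54 participants". The sampling method is "Simple random sampling from the list of eligible patients at Al Suwaiq Renal Dialysis Center"; the length of that list is not given.

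The SAP gives the flow as "Initially 132 screened → 54 enrolled → 26 participants per group in final analysis". Its primary objective is the effect of home exercise on depression and anxiety. Prevalence comes second: "Secondary Objective: To describe the baseline prevalence and severity of depression and anxiety among hemodialysis patients". The main between-group analysis is "Independent t-test for between-group differences in change scores", two-sided at 0.05. The list of results to be presented names an interval only for the within-group tests: "Paired t-test results with mean difference, 95% CI, and p-value".

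Neither document gives a target difference, an SD, a power or a dropout allowance for the randomised comparison.

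**The concern.** There are two linked problems.

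- **The figure does not follow from its inputs.** The formula and every input are stated together, so the result can be checked directly, and it fails by a wide margin. The Phase I precision that the Protocol claims is therefore unsupported.
- **The calculation does not address the main question.** A prevalence formula fixes the width of an interval around one proportion. It says nothing about a difference in mean change between two arms. The same 54 is nevertheless the number enrolled in the randomised trial, and the Protocol's expected outcomes include a statistically significant between-group reduction.

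A reader cannot tell how large a reduction the trial could detect. With no between-group interval among the listed results, a non-significant result for H2 could be taken as evidence that exercise has no effect, when the trial may only have been too small to show one.

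**Working it through.** **Inputs.** From the Protocol's sample-size section: N = 132, 95% confidence (z = 1.96), margin e = 0.05, prevalence p = 0.73, stated result 54. From the SAP: 54 enrolled, 26 per group analysed, two-sided alpha 0.05, independent t-test on change scores.

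**1. Attempt to reproduce 54.**

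- Infinite population: n0 = z²p(1−p)/e² = 1.96² × 0.73 × 0.27 / 0.05² = 0.7572 / 0.0025 = 302.9.
- Finite correction: n = n0 / (1 + (n0 − 1)/N) = 302.9 / (1 + 301.9/132) = 92.1, or 93 rounded up.
- Alternative form: n0 / (1 + n0/N) = 302.9 / (1 + 302.9/132) = 91.9, or 92 rounded up.
- With z = 2 in place of 1.96, the first form gives 93.3.

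The figure of 54 is not reproduced. The shortfall is 1 − 54/92.1 = 41%. Rounding, the form of the correction and the choice of z do not explain it.

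**2. What would give 54.** Changing one input at a time and solving back:

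| Input changed | Value needed | Value stated |
|---|---|---|
| N | about 65.5 | 132 |
| Margin | about 9.1 points | 5% |
| Prevalence | about 94% (or 6%) | 73% |
| Confidence | about 72% (z = 1.073) | 95% |

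None of these values appears in the documents. Two combinations come close: p = 0.50 with a 10% margin gives 55.8, and 90% confidence with a 10% margin and no finite correction gives 53.3. Each contradicts at least two stated elements. A slip in the calculation is also possible.

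**3. Precision that 54 delivers for a prevalence of 73%.** Margin = 1.96 × √[(0.1971/54) × (N − 54)/(N − 1)]. Only N = 132 comes from the Protocol; the other population sizes are assumptions, shown because the length of the eligible list is not given.

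| N | 95% margin |
|---|---|
| 132 | ±9.1 points |
| 100 (assumed) | ±8.1 |
| 80 (assumed) | ±6.8 |
| 66 (assumed) | ±5.1 |
| no finite correction | ±11.8 |

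These margins apply only if the 54 are the Phase I sample. If all 132 are surveyed, they do not apply and 54 is only the size of the trial.

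**4. What the randomised comparison can detect.** Two-sample t-test, two-sided 0.05, power from the noncentral t distribution, differences in units of the SD of the change score:

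- 26 per group: 80% power at 0.79 SD and 90% power at 0.92 SD.
- 27 per group (all 54 analysed, equal split assumed): 80% power at 0.78 SD.
- Approximate half-width of the 95% CI at 26 per group: t(0.975, 50 df) × √(2/26) = 2.009 × 0.2774 = 0.56 SD.
- Power at 26 per group for assumed differences, since the documents give none: 42% at 0.5 SD and 56% at 0.6 SD.

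**The case against.** The strongest defence is that the calculation belongs to Phase I. The Protocol does not rank its objectives. It lists baseline distress as the first objective and first hypothesis and gives it a phase of its own, so sizing that phase by a prevalence formula is coherent. That stands, but it narrows only the second part of the point. The arithmetic still fails, and Objective 2 and H2, which match the SAP's primary objective, still have no justification of their own.

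A second objection is that replacing the 5% margin with about 9 points fits the input to the answer. This is fair as a caution. A back-solved margin must not be presented as the one originally planned. It is sound only as the precision that 54 achieves, and the first step is to disclose what was actually used.

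A third is that 0.79 SD assumes each outcome is tested at 0.05. That is the SAP's stated level, so the figure is consistent with the plan. With two primary outcomes, a split of alpha to 0.025 each (an assumption, not in the SAP) would raise it to about 0.88 SD, so the condition should be written next to the number.

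Finally, the results list may not be exhaustive, and precision can be worked out after the fact. Both are true, but neither replaces naming an interval for the comparison that answers H2.

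**Conclusion.** The concern holds, with high confidence, and must be fixed. On the Protocol's own inputs the sample size is about 92, not 54. This needs no assumption beyond the named formula. The documents do not show which input or step is at fault.

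The loss of precision from ±5 to about ±9.1 points depends on the 54 being the survey sample and on N being 132. The SAP's flow leaves open whether Phase I covers the 54 or all 132.

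The randomised comparison has no sizing on either reading. The 0.79 SD figure uses only the planned numbers and the planned alpha per test. The powers at 0.5 and 0.6 SD are illustrations and the conclusion does not depend on them.

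**What to change.** Keep 54 and change the text.

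1. **Protocol, sample size.** State the population size, margin or other input actually used, so that inputs and result agree. If N is 132 and the survey sample is 54, replace the 5% margin with about ±9 points, labelled as the precision achieved. If 54 was set by feasibility, say so.
2. **Both documents.** State whether Phase I surveys the 54 or all 132, and that the prevalence formula supports Phase I only.
3. **SAP, study population.** State that 26 per group gives 80% power only for about 0.79 SD of the change score, at two-sided 0.05 for each outcome.
4. **SAP, presentation of results.** Add the between-group mean difference in change with its 95% CI for each score. Interpret a non-significant H2 result from that interval, not as evidence of no effect.

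The cost is wording in two documents, with no extra patients and no change to the tests. The downside is that the stated precision may look less favourable and the limited sensitivity of the trial becomes explicit.

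### The prevalence aim is worded for hemodialysis patients in general, but the only sampling frame is the exercise-eligible list, and 54 does not follow from the stated population of 132

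*Protocol*

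**What the plan says.** **Target population.** H1 in the protocol reads: "There is a high level of psychological distress among patients undergoing dialysis treatment". The SAP's secondary objective is: "To describe the baseline prevalence and severity of depression and anxiety among hemodialysis patients". Objective 1 in the protocol is worded just as broadly. None of the three is limited to people fit for an exercise programme.

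**Sampling frame.** The protocol section on sample size and sampling gives one method: "Simple random sampling from the list of eligible patients at Al Suwaiq Renal Dialysis Center". Neither document states how many names are on that list.

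**Eligibility.** The protocol section on study population asks for adults with at least three years on hemodialysis and continues: "Stable clinical status; No diabetic foot complications; Able to walk without assistance". It excludes anyone with a condition that limits exercise and anyone who declines consent. There is one set of criteria for both phases, and the SAP refers back to it.

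**Sample size.** The protocol derives 54 as follows: "Using Cochran's formula for finite populations, with a total population of 132, a 95% confidence interval, 5% margin of error", with an assumed depression prevalence of 73%. The SAP describes the same 132 differently, as "Initially 132 screened", followed by 54 enrolled and 26 per group analysed.

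**The concern.** A prevalence estimate describes the population from which the sample was drawn. Here the aim names one population (hemodialysis patients) and the frame is another (those who meet the entry criteria of a walking trial). Patients who are unstable, need help to walk, or have been on dialysis for less than three years cannot enter the sample. A percentage reported against Objective 1 or H1 would be attributed to a group that was not sampled.

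The formula has a related fault. Its population size is given as "with a total population of 132", while the sample comes from the eligible list. The SAP's word for the 132 suggests a count taken before eligibility was applied. A finite-population correction is valid only when N is the size of the list being sampled. If N is wrong, the stated precision is wrong too.

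What is at stake is the descriptive aim: Objective 1, H1 and the SAP's only secondary objective. It is also the quantity on which the sample size rests.

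**Working it through.** **Inputs, all from the protocol section on sample size and sampling:** N = 132; 95% confidence, so z = 1.96; margin e = 0.05; prevalence p = 0.73; stated result n = 54.

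**Step 1. Reproduce the plan's figure.**

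Infinite-population size: n0 = z² p(1 − p)/e² = 3.8416 × 0.73 × 0.27 / 0.0025 = 302.9.

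Finite-population size: n = n0 / (1 + (n0 − 1)/N) = 302.9 / (1 + 301.9/132) = 92.1, or 93 rounded up.

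The stated 54 is not reproduced. Variants at N = 132 do not reach it either:

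- correction written as n0/(1 + n0/N): 91.9
- z = 1.645: 81.8
- 99% confidence: 105.6
- p = 50%: 98.4

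**Step 2. Solve for the N that gives 54.**

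N = 54(n0 − 1)/(n0 − 54) = 54 × 301.9/248.9 = 65.5.

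So 54 fits a list of about 65 or 66 names. At N = 65 the formula gives 53.7, and at N = 66 it gives 54.3.

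**Step 3. Margin that 54 patients deliver.**

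Margin = 1.96 × √[ (0.73 × 0.27/54) × (N − 54)/(N − 1) ]. The length of the eligible list is not in the documents, so N is an assumption shown over a range. The last column is the n that a 5-point margin would need.

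| Eligible list N | Margin with n = 54 | n for ±5 points |
|---|---|---|
| 60 | ±3.8 | 51 |
| 66 | ±5.1 | 55 |
| 80 | ±6.8 | 64 |
| 100 | ±8.1 | 76 |
| 132 | ±9.1 | 93 |

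**Step 4. Frame against target.** Let f be the eligible share of the centre and d the prevalence among ineligible patients minus that among eligible patients. An estimate from eligible patients alone differs from the centre-wide value by (1 − f) × d. If 54 eligible patients are drawn from 132, f lies between 54/132 = 41% and 100%. The documents give neither f nor d, and d could have either sign. The difference is zero if everyone is eligible or if d = 0. No size or direction can be assigned from the plan.

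Steps 3 and 4 are separate problems. Putting the right N into the formula corrects the precision for the eligible list. It does not make the eligible list represent the whole centre.

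**The case against.** The strongest defence is that Phase I may cover all 132 patients. The sampling section does not mention Phase I, the SAP's flow treats 54 as trial enrolment, and screening could mean that all 132 complete the questionnaires. A prevalence formula could have been borrowed, wrongly, to size the trial while the survey itself takes in everyone. This reading cannot be excluded. It is tempting to answer that a census would need no survey formula and that the formula yields 54. That answer fails, because the formula with the stated inputs does not yield 54. What remains is that neither document says all 132 are surveyed, and the only frame described is the eligible list.

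A reader might also infer that the eligible patients are probably less distressed, so that prevalence will be understated by several points. The documents do not support this. They give no distress figures by mobility, stability or time on dialysis, and the three-year criterion has no documented direction of effect. Any figure for the bias would rest on two invented inputs.

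A third inference is that the calculation certainly used the wrong N. That is not established either. The figure 54 fits a list of about 65 or 66, so a shorter list may have been used and 132 misreported, or there may be an arithmetic slip. The documents do not settle which.

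It is fair to add that H1 has no threshold or test, that the prevalence aim is secondary in the SAP, and that the criteria and the single centre are openly stated. These points limit the consequence but do not remove the mismatch.

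**Conclusion.** The point holds in limited form. As written, the prevalence estimate applies to eligible, consenting patients at this centre, while Objective 1, H1 and the SAP's secondary objective are worded for hemodialysis patients in general. It goes too far to say that H1 will be answered for the wrong group. The supportable statement is that the Phase I population is not defined and the only frame given is narrower than the aim. Direction and size of any difference are unknown.

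Separately, the stated sample size and margin do not follow from the stated N. The formula gives 92 to 93 against the plan's 54, and the margin with 54 is about ±9.1 points at N = 132 against the plan's 5. The 5-point margin holds only if the eligible list has about 65 or 66 names or fewer. These figures assume p = 73%, simple random sampling and the normal approximation used by the plan's own formula.

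The randomised comparison between exercise and standard care is unaffected.

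**What to change.** 1. Restrict Objective 1, H1 and the SAP's secondary objective to the population actually sampled: clinically stable adults at this centre, on hemodialysis for at least three years, who meet the trial's mobility and exercise criteria and consent.
2. Report how many of the 132 are eligible. Use that count as N in the finite-population formula and in the 95% confidence interval for prevalence, and correct the derivation of 54.
3. Restate the margin that 54 patients deliver for that list. Do not enrol more for this purpose.
4. If Phase I is meant to cover all 132, say so, report prevalence for the whole centre split by eligibility, and remove the survey formula as the basis for 54.

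**Cost.** Items 1 to 3 change wording and recalculated figures only. The price is a narrower claim and, unless the list has about 66 names or fewer, a wider stated margin. Item 4 means up to 132 − 54 = 78 more patients completing the two questionnaires than if only the 54 are surveyed, and it leaves 54 without a stated basis. Neither route changes the randomised comparison.
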